8.4 Sample Size Analysis

8.4.1 Primary Superiority Test

The power for the MMRM tests were approximated by the power for the corresponding two-sample t-test using industry standard software.⁴⁰ Power for the t-test is a function of the magnitude of the treatment group difference relative to the standard deviation of change scores. Preliminary data to evaluate clinical effect size was available from the safety and efficacy pilot study (BB-IDE 14796). In 15 patients per group, the mean (SD) WOMAC Pain Total score for the ACP and control groups at 6 months post-treatment were 2.5 (3.6) and 9.1(3.2) respectively. At screening, the baseline mean (SD) values were 10.2 (1.8) and 10.5 (2.0). Therefore, the large difference at Month 6 is not explainable by baseline differences. These data imply a treatment group difference in mean improvements equal [10.2-2.5=7.7] minus [10.5-9.1=1.4] = 6.3 in favor of ACP and a standard deviation of approximately equal to 3.4. This standard deviation also applies to change from baseline if the correlation between baseline and change scores is equal to 0.5. Given the small sample size of the pilot study, a 95% two-sided confidence interval for the true difference was determined to be (-9.0 to -4.2) in order to account for the uncertainty in estimated treatment group mean differences. Specifically, on the basis of the pilot study, a superiority treatment group differences as small as -4.2 cannot be statistically ruled out. Therefore, as -4.2 represents a conservative estimate of the treatment group difference for purpose of sample size analysis. Under these assumptions, the standardized mean difference (Cohen's effect size) is equal to 1.235. This effect size is typically considered very large. Cohen's benchmark for a large effect size in the behavioral sciences is 0.80. In order to mitigate against any potential bias present in the preliminary study, the expected effect size is further reduced from 1.235 to 0.80. From another perspective, a treatment group difference of -4.2 in mean improvements is clinically significant as follows. The mean WOMAC Pain prior to surgery is slightly more than 10 (range 0 to 20). Therefore, a treatment group difference of -4.2 in the mean improvement in WOMAC Pain score represents about a 40% treatment group difference in the mean percent improvements. A group difference

in mean percentage changes so large is likely clinically significant given the known reliability and validity of the WOMAC Pain score.

Randomization will be 2:1 in order to increase precision when characterizing the safety profile of the investigational treatment. We assume a one-sided type 1 error of α =0.025 and a standardized mean difference of 0.80 and determined that a total sample size of N=78 (52 ACP and 26 control) patients are required for 90% power. **This value is increased by 15% to N=90 (60 ACP and 30 control)** to account for potential loss-to-follow-up or other exclusions from the primary effectiveness analysis set.

8.4.2 Conditional Superiority Test

Among 15 patients per group, the mean (SD) WOMAC Function score for the ACP and control groups at 6 months post-treatment were 7.9 (11.7) and 31.3 (12.0), respectively. At screening, the baseline mean (SD) values were 32.1 (9.5) and 31.4 (10.2). Therefore, the large difference at Month 6 is not explainable by baseline differences. These data imply a treatment group difference in mean improvements equal [31.1-7.9=23.2] minus [31.3-31.4=-0.1] = 23.3 in favor of ACP and a standard deviation approximately equal to 11.9. Given the small sample size of the pilot study, a 95% two-sided confidence interval for the true difference was determined to be (-31.9 to -14.9). Therefore, the pilot study cannot rule out treatment group differences as small as -14.9 and so -14.9 represents a conservative estimate of the treatment group difference for purpose of sample size analysis

Under these assumptions, the standardized mean difference (Cohen's effect size) is equal to 14.9/11.9=1.25 which is nearly the same as observed for WOMAC Pain scores. For the same reason stated above, the study will be designed to detect an effect size of 0.80 with 90% power and the same final sample size of N=78 (52 ACP and 26 control) patients increased by 15% to N=90 (60 ACP and 30 control) to account for potential loss-to-follow-up or other exclusions is assumed.

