The study is designed to permit an additional labeling claim beyond reduction in pain while maintaining control of type 1 error. The additional labeling claim concerns improvement in patient function. This will be measured using change from baseline to Month 6 (180 days) in the WOMAC Function score. In order to control type 1 error for this study, these two hypotheses were hierarchically specified. First, the primary endpoint concerning WOMAC pain will be tested. If the 1-sided p-value ≤ 0.025 , it will be concluded that the investigational treatment is superior to control in terms of pain reduction and the study will be considered as having met its Study Success criterion. In this case, additionally, the treatment group difference in mean change from baseline to Month 6 (180 days) will also be tested for the WOMAC Function score using a 1-sided p-value ≤ 0.025 . Testing of the conditional endpoint is contingent on demonstrating superiority in terms of WOMAC pain and it is not intended to require superiority in both WOMAC Pain and WOMAC Function for Study Success.

3.2.3 Primary and Conditional Endpoints:

The primary and conditional endpoints of WOMAC Pain and Function will be assessed at 6 months (180 days) post-treatment. All subjects will continue to be followed out to 12 months (365 days) post-treatment. When the last patient reaches the 6-month (180 days) time point, all available data will be reported to FDA. Note: Subjects will remain blinded to their randomized treatment throughout the study.

3.2.4 Secondary Endpoints:

WOMAC Total, (Pain, Function, Stiffness) Scores 2 (60 days), 3 months (90 days) and 12 months (365 days) and changes to these.

WOMAC Stiffness Score at Month 6 (180 days) and changes to Month 6 (180 days).

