8.2 Conditional Effectiveness Hypothesis for Function

The study is designed to permit an additional labeling claim beyond reduction in pain while maintaining control of type 1 error. The additional labeling claim concerns improvement in patient function. This will be measured using change from baseline to Month 6 in the WOMAC Function score. In order to control type 1 error for this study, these two hypotheses were hierarchically specified. First, the primary endpoint concerning WOMAC pain will be tested. If the 1-sided p-value ≤ 0.025 , it will be concluded that the investigational treatment is superior to control in terms of pain reduction and the study will be considered as having met its Study Success criterion. In this case, additionally, the treatment group difference in mean change from baseline to Month 6 will also be tested for the WOMAC Function score using a 1-sided p-value ≤ 0.025 . Testing of the conditional endpoint is contingent on demonstrating superiority in terms of WOMAC Pain and it is not intended to require superiority in both WOMAC Pain and WOMAC Function for Study Success.

The conditional effectiveness hypothesis for this study is that ACP treatment is superior to control in terms of mean change from baseline to Month 6 in the WOMAC Function score. Symbolically, the null and alternative hypotheses may be expressed as follows:

```
Ho: \delta(\text{function})_{ACP} - \delta(\text{function})_{Control} \le 0
Ha: \delta(\text{function})_{ACP} - \delta(\text{function})_{Control} > 0
```

Where $\delta(function)_{ACP}$ and $\delta(function)_{Control}$ are the expected mean changes from baseline to Month 6 in the WOMAC Function score among patients in the ACP and control groups, respectively.

Formal testing of the conditional endpoint will only take place if the null hypothesis involving the primary endpoint is rejected at 1-sided alpha=0.025. In that case, the null hypothesis concerning the conditional endpoint will be tested, also at 1-sided alpha=0.025. By structuring the hypothesis testing hierarchically and by the 'closed testing principle' no multiplicity adjustment is necessary.

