8.3.2 Covariates in MMRM

The MMRM model must contain an indicator variable for treatment group, a categorical time factor, and treatment group by time interaction. It is also necessary to include to the baseline value of the WOMAC outcome variable (either pain or function) so that significance levels will apply equally to values over time and to changes from baseline. Often a factor for site is included in the MMRM to account for randomization within site. Given the modest sample size and in

response to FDA Advisory items c.1.b (dated July 23, 2015), site will not be included in the primary MMRM. Instead, the impact of site heterogeneity on estimated treatment group differences will be evaluated in supporting analyses by introducing an additional random effect as described below.

It is often considered useful to include additional baseline covariates in order to further reduction of potential bias due from missing values. Candidate variables include age, gender, BMI, and prior analgesic use. However, in response to FDA Advisory item c.1.b, these variables will not be included in the primary MMRM model. Instead, additional baseline covariates will be added to the model in exploratory analyses only if any of these variables appear with clinically significant imbalance between treatment groups. The purpose of these analyses would to be determine the extent to which such imbalance impacts on estimated treatment group differences and associated significance levels.

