8.8.6 Treatment of Missing Data

All patients contributing at least one follow-up WOMAC Total score will be included in the primary superiority test through the use of the mixed model for repeated measures (MMRM) in the mITT analysis set. In this way patients with incomplete follow-up are retained and contribute to the primary superiority test.

As noted elsewhere, FDA has previously recommended to not include many baseline covariates in the MMRM due to the modest sample size. Therefore, the only baseline covariates available for implicit imputation of changes from baseline to Month 6 (180 days) is the baseline value itself and treatment group. It follows then, that for the ITT analysis, the MMRM will implicitly impute missing changes from baseline to Month 6

(180 days) for patients with no follow-up data as the within treatment group mean change score modified by the effect of the baseline value

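### Does the 90% power in section 8.4.2 overstate the chance of supporting the Function claim, given that Function is tested only after Pain succeeds?

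*Combined protocol and SAP*

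**What the plan says.** Section 8.4.1 sets the basis of the power figures: "The power for the MMRM tests were approximated by the power for the corresponding two-sample t-test using industry standard software". It plans on a cautious effect for Pain: "the expected effect size is further reduced from 1.235 to 0.80". At one-sided 0.025 and 2:1 allocation this leads to 78 evaluable patients (52 and 26) for 90% power. The total is raised to 90 (60 and 30) "to account for potential loss-to-follow-up or other exclusions from the primary effectiveness analysis set".

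Section 8.4.2 carries this over to Function: "For the same reason stated above, the study will be designed to detect an effect size of 0.80 with 90% power", with the same 78 raised to 90.

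Section 8.2 sets the order of testing: "Formal testing of the conditional endpoint will only take place if the null hypothesis involving the primary endpoint is rejected at 1-sided alpha=0.025". Sections 3.2.2 and 8.2 both add that "it is not intended to require superiority in both WOMAC Pain and WOMAC Function for Study Success".

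On the analysis model, section 8.3.2 says: "It is also necessary to include to the baseline value of the WOMAC outcome variable (either pain or function"). Section 8.8.6 says of the mixed model: "In this way patients with incomplete follow-up are retained and contribute to the primary superiority test".

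**The concern.** Function is the extra labeling claim that the study is designed to permit, and 8.4.2 is the only place that gives a power for it. The claim needs a significant Pain result and then a significant Function result. With equal effect sizes, and any correlation below 1 between the two test statistics, the chance of both is lower than the chance of either alone. A reader could take 90% at 78 patients as the chance of supporting the Function claim, when the calculation behind it covers one test. If the true figure were clearly lower, the sponsor would be planning a labeling claim on too favourable a number.

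**Working it through.** **Inputs from the plan.** Effect size 0.80 on both endpoints, one-sided alpha 0.025, 52 and 26 evaluable (60 and 30 randomized), two-sample t-test (8.4.1, 8.4.2). Pilot SDs: Pain 1.8 and 2.0 at baseline, with 3.4 used for planning; Function 9.5 and 10.2 at baseline, with 11.9 used for planning.

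**Assumed.** The pain-function correlation, rho, is not in the documents. The range 0.5 to 0.9 is shown.

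**1. The plan's own figure.** The noncentrality is 0.80 / sqrt(1/52 + 1/26) = 3.331, with 76 degrees of freedom and critical value 1.992. Power is 90.8%. At 50 and 25 it is 89.7%, so 78 is the smallest 2:1 total that reaches 90%. The stated 90% is the power of a single test, and it is correct.

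**2. Both tests, no baseline adjustment.** Joint power is P(Z1 < q, Z2 < q) for a bivariate normal with correlation rho, where q is the normal quantile of the single-test power (90.8% at 52/26, 94.3% at 60/30).

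| rho | 52/26 | 60/30 |
|---|---|---|
| 0 | 82.4% | 88.9% |
| 0.5 | 84.5% | 90.0% |
| 0.7 | 85.8% | 90.9% |
| 0.8 | 86.7% | 91.5% |
| 0.9 | 87.9% | 92.2% |

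Simulation of correlated endpoints (200,000 trials per correlation) at 52/26 gives 84.6%, 85.9%, 86.5% and 87.9% for rho 0.5, 0.7, 0.8 and 0.9.

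**3. How much of the loss allowance is needed.** Solving for joint power of 90% gives a total of 89.9, 87.6, 85.8 and 83.2 evaluable at rho 0.5, 0.7, 0.8 and 0.9. Of the 12 patients added to 78, that is 11.9, 9.6, 7.8 and 5.2. Nearly all are needed at rho 0.5 and fewer than half at 0.9.

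**4. With the planned baseline covariate.** Pooled baseline SDs are sqrt((1.8² + 2.0²)/2) = 1.90 for Pain and sqrt((9.5² + 10.2²)/2) = 9.86 for Function. The planning SDs of 3.4 and 11.9 match the pooled month 6 SDs: sqrt((3.6² + 3.2²)/2) = 3.4 and sqrt((11.7² + 12.0²)/2) = 11.9. Sections 8.4.1 and 8.4.2 apply them to differences in mean improvement, that is, to change scores.

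If change and month 6 scores have the same SD, the baseline-change correlation has magnitude c = (baseline SD) / (2 × month 6 SD):

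- Pain: 1.90 / 6.8 = 0.28
- Function: 9.86 / 23.8 = 0.41

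Taking 0.80 as the unadjusted effect, adjustment raises it to 0.80 / sqrt(1 − c²):

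- Pain: 0.80 / sqrt(1 − 0.28²) = 0.833
- Function: 0.80 / sqrt(1 − 0.41²), about 0.88

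With rho now the correlation of the adjusted outcomes, joint power at 52/26 is 89.5% (rho 0.5), 90.3% (0.7) and 91.7% (0.9). Simulated analyses of covariance give about 89%, 90% and 91% to 92%. They run slightly lower because they include chance baseline imbalance and the lost degree of freedom.

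**5. A larger Pain effect.** With Function held at 0.80, 52/26 and no adjustment, joint power for rho 0.5 to 0.9 is 88.3% to 90.3% at a Pain effect of 0.9, 90.0% to 90.8% at 1.0, and 90.8% at 1.235.

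**The case for a change.** The strongest case for a change is that the plan's power method is the unadjusted t-test and its stated effect is 0.80 on both endpoints. On those inputs alone, power through the sequence at 78 patients is 2 to 5.5 points below 90% for rho 0.5 to 0.9. The direction does not depend on the assumed correlation. The word conditional in the section title names the order of testing and does not say which power is meant. Nor is 90% the power given a Pain success, which would be about 93% to 97%. A few added sentences would cost little.

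Most of this stands as arithmetic, and it is true that no sentence in 8.4.2 says the figure is for Function alone. But 8.4.1 has already defined the power figures as those of the corresponding t-test, and that is the power of one test. Quoting each test's power separately in a fixed sequence is ordinary practice, and the order is stated openly in 3.2.2 and 8.2. Adding only the 84% to 88% range would also mislead, because it leaves out a covariate that the model must contain. It further sets aside that the mixed model keeps patients with partial follow-up, so with loss as planned the information lies between that of 78 and 90 complete patients.

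**Conclusion.** No change is needed. The 90% in 8.4.2 is correct for the test it describes (90.8%), and no passage states or implies a different probability that turns out to be wrong. Through the sequence at 78 evaluable patients, power is about 84% to 88% by the unadjusted approximation, or about 89% to 92% with the planned baseline adjustment. At 90 evaluable it is 90% to 92% even without adjustment.

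These ranges rest on an assumed pain-function correlation of 0.5 to 0.9 and an effect of 0.80 on both endpoints. The adjusted range also assumes that the plan's SDs apply to change scores, and they come from a pilot with 15 patients per group. The shortfall disappears if the Pain effect is about 1.0 or more; the plan cut its value to 0.80 from 1.235, which was already based on a confidence limit.

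Sample size, alpha, test order, type 1 error, analysis and Study Success are the same whichever power is quoted, and Study Success does not require Function. This is a missing label. Noting in 8.4.2 that the figure is for the Function test alone would be harmless but would alter no decision. If a power for both tests were ever quoted, it should be shown with and without baseline adjustment and with the assumed correlation stated.

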8.5 Secondary Endpoints

The following will be summarized in descriptive analyses:

- WOMAC Stiffness Score at Month 6 and changes to Month 6
- WOMAC Total, (Function, Pain, Stiffness Scores) at 2 (60 days), 3 (90 days), and 12 months (365 days) and changes to these time points.

There will be no adjustment for multiplicity for the secondary endpoints.

8.6 Concomitant Analgesics/Treatment

Use of medication for joint pain will be recorded at each study visit according to, category (OTC NSAID, prescription NSAID, acetaminophen, and narcotic). The

use of analgesic at 6 months (180 days) will be evaluated as an exploratory endpoint in the descriptive analyses. The data collected will include medication name and the total daily dose. Additionally, concomitant treatments (e.g., physical therapy) will be recorded at each evaluation visit.

8.7 Safety Endpoints

The primary safety endpoints for this study are based on adverse events. Details regarding analyses of adverse events are provided below. Briefly, adverse event endpoints will include, but are not limited to, the following patient specific endpoints:

- Any adverse event (per patient)
- Any treatment related AE
- Any serious AE
- Any serious AE that is treatment related
- Patient death

Specific endpoints such discomfort and pain, erythema, swelling, bruising, hemorrhage, and papules will be compared between treatment groups in terms of both per patient incidence rates and total counts. Fisher's exacts tests will be used to provide descriptive comparisons between incidence rates. Counts of AEs will be displayed overall and over time.

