3.2.5 Safety Endpoint

Adverse events will be compared between ACP treatment and the control in terms of both per patient incidence and total.

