8.8 Safety Analysis

Assessment of safety will be based primarily on the incidence and severity of complications and adverse reactions associated with the treatment. Adverse event rates will be summarized by type of AE and for specific AEs in two ways: 1) per patient using counts and percentages and 2) by event, summarizing event counts by visit interval over time. Treatment and procedure related events will be summarized by severity. Events listings will be provided that include details such as relatedness, severity, onset and resolution status will be provide for all events and for relevant subsets of events such as serious events and related events. All safety endpoints will be summarized separately for investigational and control groups. Incidence rates for grouped and individual adverse events will be compared using counts, percentages, and descriptive Fisher's exact test nominal p-values. Grouped adverse events will include events at least possibly related to study treatment and serious adverse events.

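### Adverse-event totals are compared between arms of 60 and 30 patients without a denominator, so equal event rates give an expected 2:1 ratio in a descriptive summary

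*Combined protocol and SAP*

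**What the plan says.** Section 3.2.5 (Safety Endpoint) states: "Adverse events will be compared between ACP treatment and the control in terms of both per patient incidence and total". The Protocol Summary repeats this. Section 8.7 (Safety Endpoints) first lists patient-level endpoints: any event, related, serious, serious and related, and death. It then adds that named reactions such as pain, swelling and bruising "will be compared between treatment groups in terms of both per patient incidence rates and total counts". On method it says "Fisher's exacts tests will be used to provide descriptive comparisons between incidence rates", and for the counts only "Counts of AEs will be displayed overall and over time".

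Section 8.8 (Safety Analysis) summarises rates "1) per patient using counts and percentages and 2) by event, summarizing event counts by visit interval over time". Section 8.9 (Adverse events counts over time) puts counts of systemic events on a per-patient footing and all other events on a per-procedure footing.

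Section 8.4.1 fixes the allocation and gives the reason: "Randomization will be 2:1 in order to increase precision when characterizing the safety profile of the investigational treatment". The planned arms are 60 ACP and 30 control. Section 8.8.1 assigns safety analyses to the As Treated set.

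**The concern.** A raw event total depends on how many patients were observed as well as on how often they had events. With twice as many patients on ACP, a side-by-side comparison of totals makes ACP look worse by design, even when the treatments are equally safe. Unequal allocation was chosen to describe the safety of ACP more precisely, so a summary that reads against ACP only because of that allocation works against its purpose.

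Totals are in the plan for a good reason. Each patient is due three injections, and local reactions can recur. Per-patient incidence counts a patient once, so recurrence shows only in event counts. Those counts therefore need a stated denominator. No section specifies an event rate, a rate ratio or patient-time.

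**Working it through.** **Arm sizes (section 8.4.1).** The method is a two-sample t-test with one-sided alpha 0.025, standardised difference 0.80 and 2:1 allocation. With the noncentral t distribution:
- 50 + 25 patients give power 0.897.
- 52 + 26 patients give power 0.908.

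The stated N = 78 is therefore the smallest 2:1 design that reaches 90% power. Then 78 × 1.15 = 89.7, rounded to 90 = 60 + 30. The plan's figure is reproduced and is not in dispute.

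**Expected totals under equal safety.** Let r be the number of events per patient, the same in both arms, with equal follow-up. The documents give no adverse-event rate, so r is an assumption. Expected total = patients × r.

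| r | ACP (60r) | Control (30r) | Ratio |
|---|---|---|---|
| 0.5 | 30 | 15 | 2.0 |
| 1 | 60 | 30 | 2.0 |
| 2 | 120 | 60 | 2.0 |

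The ratio 60r/30r = 2.0 does not depend on r. Dividing by patients (60 and 30), by planned injections (3 × 60 = 180 and 3 × 30 = 90), or by patient-time at equal follow-up brings it to 1.0.

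**How often the ACP total would be the larger.** If totals are Poisson (assumption), P(ACP total > control total) under equal rates is:
- 0.93 at r = 0.25
- 0.986 at r = 0.5
- above 0.999 at r = 1

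If control has 0.5 events per patient and the ACP rate is 30% lower, the expected totals are 60 × 0.35 = 21 and 30 × 0.5 = 15. ACP still shows the larger total with probability 0.82. With overdispersed patient counts (negative binomial, variance = mean + mean², assumption), the probabilities for r = 0.5 and for the 30% reduction are 0.96 and 0.78. The direction does not depend on the Poisson assumption.

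**Visit intervals.** The nominal visit days 0, 7, 14, 60, 90, 180 and 365 give intervals of 7, 7, 46, 30, 90 and 185 days. The longest is 185/7 = 26.4 times the shortest. At an assumed constant rate of one event per patient-year in both arms:
- First week: 60 × 7/365 = 1.15 v 30 × 7/365 = 0.58, ratio 2.0.
- Month 6 to Month 12: 60 × 185/365 = 30.41 v 30 × 185/365 = 15.21, ratio 2.0.

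The between-arm ratio is the same in every interval.

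**The case against.** The strongest reply is that nothing in the trial depends on the totals. Study success rests on WOMAC Pain. The listed safety endpoints are patient-level, the only safety test is Fisher's exact test on incidence, and even that is descriptive. No rule judges safety by which total is larger, and anyone who knows the allocation can divide by 60 and 30. All of this stands, and it keeps the point minor.

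The second reply is section 8.9. Local reactions are not systemic, so on a plain reading their counts over time are put on a per-procedure footing. Whether a procedure means one injection (180 v 90) or the whole series (60 v 30), the expected ratio under equal safety is 1.0. A reader might otherwise infer that no planned output deals fairly with repeated events; section 8.9 does not support that. It does not settle the matter either. It concerns counts over time, and it is not tied to the totals in 3.2.5 and 8.7 or to the interval counts in 8.8. It does not define a procedure for this trial, and neither footing accounts for differing follow-up.

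A reader might also infer that the very unequal visit intervals add to the distortion between arms. They do not, because both arms follow the same schedule. Interval length affects only how the time pattern within an arm is read, and planned listings with onset help there.

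**Conclusion.** The point holds as a minor one. The Protocol Summary, 3.2.5 and 8.7 (Safety Endpoints) include a comparison of raw event totals with no denominator. Under equal per-patient rates that comparison has an expected ACP-to-control ratio of 2.0. This figure rests on the planned 60 and 30 patients and on equal follow-up; differential dropout would move it. It needs no assumption about the event rate. The probabilities that ACP shows the larger total do rest on assumed rates and distributions, and serve as illustration only.

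It would go too far to say that the main safety comparison is biased. Per-patient incidence is unaffected by the allocation ratio, and it is the only quantity tested. The defect is a missing denominator in one descriptive summary, together with 8.7 and 8.8 not being joined to 8.9.

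**What to change.** - **Sections 3.2.5, 8.7 (Safety Endpoints) and 8.8 (Safety Analysis), with the Protocol Summary to match:** replace the comparison of totals by events per patient (per injection for local reactions) and events per patient-month of follow-up, in the As Treated set.
- **Estimate:** give one overall ACP/control rate ratio with a 95% confidence interval that allows for repeated events within a patient. A negative binomial model with log follow-up time as offset would do, as would a Poisson model with robust standard errors. Label it descriptive.
- **By-interval tables:** show the number at risk and the patient-time beside each count. Fit no model per interval; with about 30 controls and 7-day intervals the counts are likely to be too sparse for stable estimates.
- **Raw totals:** keep them as a listing only.
- **Section 8.9:** define what a procedure means here, and state how its per-patient and per-procedure summaries relate to the counts in 8.7 and 8.8.

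The cost is one extra descriptive table and a small amount of SAP wording. Event dates, visit dates, treatment forms and the date of last visit or discontinuation are already on the case report forms, so no new data are needed.
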